Appendix D. Study Activities – Post-Treatment (PT) Period

Activity	PT Wk 4	PT Wk 12	PT Wk 24 or PT D/C ^a
Vital Signs and Weight	X	X	X
Hematology/Chemistry/Urinalysis/Coagulation Panel	X		X ^b
Total Insulin		X	
Pregnancy Test (urine) ^c	X (u)		X (u) ^b
Concomitant Medication Assessment	X	X ^d	X ^d
Child-Pugh Score ^e		X	X
Adverse Event Assessment	X ^f	X ^g	X ^g
HCV RNA Samples	X	X	X
HCV Resistance Sample	X	X	X
Archive Plasma Sample	X	X	X
Pharmacogenetic DNA and RNA Sample (optional)		X	
Patient Reported Outcomes Instruments (PROs) ^h		X	
HCC Screening Liver Ultrasound			X ⁱ

Wk = Week; PT D/C = Post-Treatment Discontinuation

- Subjects who prematurely discontinue from the Post-Treatment Period should return to the site to complete the PT D/C Visit procedures.
- Hematology/Chemistry/Urinalysis/Coagulation Panel and Pregnancy Test are not required at PT Wk 24, but only at PT D/C if subject discontinued prior to PT Wk 4.
- Urine pregnancy testing is not required in the PT period for women that are not of childbearing potential.
- Only medications associate with HCV treatment or taken for a serious adverse event (SAE) will be collected after 30 days post-dosing.
- Only for subjects in Arm B (compensated cirrhosis).
- Nonserious AEs and all SAEs will be collected until 30 days post dosing.
- Only SAEs will be collected thereafter as described in Section 6.1.4.

- h. PROs should be administered before any study procedures in the order listed in Section 5.3.1.1.
- i. HCC Screening Liver Ultrasound performed only for subjects in Arm B (compensated cirrhotic) as described in Section 5.3.1.1.

Note: Day 1 of the Post-Treatment Period will be defined as the day after the last dose of study drug.

Appendix E. Protocol Amendment: List of Changes

The summary of changes is listed in Section 1.1.

Specific Protocol Changes

Section 1.3 List of Abbreviations and Definition of Terms

Subsection Abbreviations

Delete:

sAFP Alpha fetoprotein

Section 3.0 Introduction

Subsection GLE and PIB

First paragraph, first and second sentence previously read:

In general, GLE and PIB combination has been well tolerated when administered to over 800 healthy volunteers and 500 HCV-infected subjects. The efficacy rates were high (> 95%) among treatment-naïves or pegIFN + RBV-experienced noncirrhotic HCV-infected GT-1 – 6 subjects treated with 8 weeks of GLE/PIB in Phase 2 studies

Has been changed to read:

In general, GLE and PIB combination has been well tolerated when administered to over 800 healthy volunteers and 2,376 subjects were randomized or enrolled in the registrational studies or supportive Phase 2 studies to receive GLE 300 mg QD and PIB 120 mg QD. Of these, 2,369 subjects received at least 1 dose of study drug. The efficacy rates were high (> 95%) among treatment-naïve or pegIFN + RBV-experienced non-cirrhotic HCV-infected GT-1 – 6 subjects treated with 8 weeks of GLE/PIB in Phase 2 studies.

Section 3.0 Introduction

Subsection GLE and PIB

Eighth, ninth and tenth paragraph previously read:

In Part 1 of Study M14-868, no subject has experienced on treatment virologic failure or post-treatment relapse among the 74 subjects with HCV GT2 infection. Excluding

one subject who was lost to follow-up, all 73 subjects with HCV GT2 infection achieved SVR₁₂. The SVR₁₂ rates for each of the treatment regimens were 96% (24/25) (including a subject who was lost to follow-up) of subjects treated with GLE 300 mg QD + PIB 120 mg QD for 12 weeks, 100% (24/24) of subjects treated with GLE 200 mg QD + PIB 120 mg QD for 12 weeks and 100% (25/25) of subjects treated with GLE 200 mg QD + PIB 120 mg QD + RBV for 12 weeks.

In Part 1 of Study M14-868, 121 subjects with HCV GT3 infection were treated with GLE 300 mg and PIB 120 mg without ribavirin for 12 weeks and 93.3% (28/30 subjects) achieved SVR₁₂. One subject in this arm experienced relapse at Post-Treatment Week 4 and one subject had missing SVR₁₂ data.

To date, safety data across all arms in Part 1 of Studies M14-867 and M14-868 encompassing 274 subjects treated with GLE at doses 200 and 300 mg and PIB at doses 40 and 120 mg (with and without RBV in Study M14-868) for 12 weeks show that the most frequently reported adverse events were fatigue, nausea, and headache (occurring in > 5% of subjects). Most of them were Grade 1 or 2 in severity.

Has been changed to read:

To date, safety data across all arms in Part 1 of Studies M14-867 and M14-868 encompassing 276 subjects treated with GLE at doses 200 and 300 mg and PIB at doses 40 and 120 mg (with and without RBV in Study M14-868) for 12 weeks show that the

most frequently reported adverse events were fatigue, nausea, and headache (occurring in > 5% of subjects). Most of them were Grade 1 in severity.

Section 3.0 Introduction

Subsection GLE and PIB

Thirteenth paragraph, first and second sentence previously read:

Of the 274 subjects, there have been 4 (1.5%) treatment-emergent SAEs reported in Studies M14-867 and M14-868 combined (all assessed as not related to GLE or PIB): metastatic prostate cancer, pneumonia, atrial fibrillation, and B-cell lymphoma and one SAE that was not treatment-emergent (spontaneous abortion – also assessed as not related). Two subjects (0.7%; 2/274) had treatment-emergent adverse events leading to treatment discontinuation.

Has been changed to read:

Of the 276 subjects, there have been 4 (1.5%) treatment-emergent SAEs reported in Studies M14-867 and M14-868 combined (all assessed as not related to GLE or PIB): metastatic prostate cancer, pneumonia, atrial fibrillation, and B-cell lymphoma and one SAE that was not treatment-emergent (spontaneous abortion – also assessed as not related). Two subjects (0.7%; 2/276) had treatment-emergent adverse events leading to treatment discontinuation.

Section 5.2.3.2 Concomitant Therapy

Last paragraph previously read:

During the Post-Treatment Period, investigators should reassess concomitant medications/supplements and subjects may resume previously prohibited medications/supplements or revert to pre-study doses, 30 days following discontinuation of study drug, if applicable.

Has been changed to read:

During the Post-Treatment Period, investigators should reassess concomitant medications/supplements and subjects may resume previously prohibited

medications/supplements or revert to pre-study doses, 14 days following discontinuation of study drug, if applicable.

Section 5.2.3.3 Prohibited Therapy

Previously read:

Subjects must be able and willing to safely discontinue any prohibited medications or supplements listed in Table 1 at least 2 weeks or 10 half-lives (whichever is longer) prior to the first dose of any study drug and not use these during the entire Treatment Period and for 30 days following discontinuation of study drug.

Table 1. Prohibited Medications and Supplements

Medication or Supplement Name
Any herbal supplements (including milk thistle), red yeast rice (monacolin K), St. John's Wort
Carbamazepine, phenytoin, pentobarbital, phenobarbital, primidone, rifabutin, rifampin
Atorvastatin, lovastatin, simvastatin*
Astemizole, cisapride, terfenadine

* Some HMG-CoA reductase inhibitors (including atorvastatin, lovastatin, or simvastatin) should not be taken with the study drug. Subjects receiving these statins should either switch to pravastatin or rosuvastatin prior to the first dose of study drug or may interrupt statin therapy throughout the treatment period and until 30 days after the last dose of study drug, based on investigator's judgment. If switching to or continuing pravastatin or rosuvastatin, it is recommended to reduce the pravastatin dose by 50% or limit the rosuvastatin dose to 10 mg QD when taking with the study drug.

Use of ethinyl estradiol containing oral contraceptives with the GLE and PIB combination was associated with ALT increases in some healthy female subjects. Hormonal contraceptives (including oral, topical [including vaginal rings], injectable, or implantable varieties) and hormonal replacement therapy containing ethinyl estradiol may not be used from 2 weeks prior to the first dose of GLE/PIB until 30 days after the end of GLE/PIB dosing. Progestin-only contraceptives and hormonal replacement therapy, such as those containing norethindrone, desogestrel, or levonorgestrel, without ethinyl estradiol, may be used with GLE/PIB. Post-menopausal hormone replacement therapy, such as with esterified or conjugated estrogens, i.e., not containing ethinyl estradiol, may be used with GLE/PIB at the discretion of the Investigator.

The chronic use of systemic immunosuppressants is prohibited from 2 weeks prior to the first dose of study drug and until 30 days after the last dose of study drug including, but not limited to, corticosteroids (prednisone equivalent of > 10 mg/day for > 2 weeks), azathioprine, or monoclonal antibodies (e.g., infliximab).

Has been changed to read:

Subjects must be able and willing to safely discontinue any prohibited medications or supplements listed in [Table 1](#) at least 2 weeks or 10 half-lives (whichever is longer) prior to the first dose of any study drug and not use these during the entire Treatment Period and for 14 days following discontinuation of study drug.

Table 1. Prohibited Medications and Supplements

Medication or Supplement Name
Red yeast rice (monacolin K), St. John's Wort
Carbamazepine, phenytoin, pentobarbital, phenobarbital, primidone, rifabutin, rifampin
Atorvastatin, lovastatin, simvastatin*
Ethinyl estradiol
Astemizole, cisapride, terfenadine

* Some HMG-CoA reductase inhibitors (including atorvastatin, lovastatin, or simvastatin) must not be taken with the study drug. Subjects receiving these statins must discontinue the prohibited statin at least 14 days or 10 half-lives (whichever is longer) prior to the first dose of study drug and, based on investigator's judgment, (a) switch to pravastatin or rosuvastatin or (b) interrupt statin therapy throughout the treatment period and until 14 days after the last dose of study drug. If treating with pravastatin or rosuvastatin, it is recommended to reduce the pravastatin dose by 50% or limit the rosuvastatin dose to 10 mg QD when taking with the study drug.

Contraceptives and/or hormonal replacement therapies containing only progestins (such as those containing norethindrone, desogestrel, or levonorgestrel), or those containing progestins with non-ethinyl estradiol estrogens (e.g., esterified or conjugated) may be used with GLE/PIB at the discretion of the Investigator.

The chronic use of systemic immunosuppressants is prohibited from 2 weeks prior to the first dose of study drug and until 30 days after the last dose of study drug including, but

not limited to, corticosteroids (prednisone equivalent of > 10 mg/day for > 2 weeks), azathioprine, or monoclonal antibodies (e.g., infliximab).

Table 2. Clinical Laboratory Tests
Column "Clinical Chemistry," test "Albumina" previously read:

Albumina

Has been changed to read:

Albumin^a

Table 2. Clinical Laboratory Tests
Column "Other Tests"
Delete:

Alpha Fetoprotein (sAFP)^h

Table 2. Clinical Laboratory Tests
Delete: table note "h."

Performed only for subjects in Arm B as described in Section 5.3.1.1.

Section 5.3.1.1 Study Procedures
Subsection Hepatocellular Carcinoma Screening: Liver Ultrasound and Alpha Fetoprotein
Subsection title and text previously read:

Hepatocellular Carcinoma Screening: Liver Ultrasound and Alpha Fetoprotein

Subjects with compensated cirrhosis who do not have a historical qualifying liver ultrasound, CT, or MRI will have an ultrasound performed during Screening. A positive ultrasound result suspicious for HCC will be confirmed with CT scan or MRI during Screening. Suspicious ultrasound lesions confirmed by CT or MRI are exclusionary. Subjects with compensated cirrhosis will have alpha fetoprotein assayed at the visits indicated in Appendix C and Appendix D.

Has been changed to read:

Hepatocellular Carcinoma (HCC) Screening: Liver Ultrasound

HCC screening will be required as a protocol-specified study procedure only at the Screening Visit and at Post-Treatment Week 24, as indicated in [Appendix C](#) and [Appendix D](#), for subjects with compensated cirrhosis only. In-between those visits, HCC screening should be performed according to standard of care.

At the Screening Visit and at Post-Treatment Week 24, subjects with compensated cirrhosis will be required to undergo a liver ultrasound to screen for HCC, unless the subject has a historical liver ultrasound, CT scan or MRI performed for HCC screening within 3 months prior to those visits, in which case the result of the historical ultrasound, CT scan or MRI will be used as the result for the Study Visit assessment. A positive ultrasound result suspicious of HCC will be confirmed with CT scan or MRI. Alternate methods of screening for HCC (i.e., CT scan or MRI) at a study visit should be discussed with the study designated physician.

Section 5.3.2.1 Collection of Samples for Analysis

Bullet, first sentence previously read:

At all Treatment-Period visits: a single sample (4 mL) will be collected without regard to the time of dosing.

Has been changed to read:

At all Treatment-Period visits: a single sample (3 mL) will be collected without regard to the time of dosing.

Section 5.6.4.1.1 GLE and PIB Dose and Treatment Duration

Delete: last paragraph

The maximum dose of GLE/PIB will not exceed 300 mg/120 mg per day for up to 12 weeks.

Section 7.0 Protocol Deviations

Contact information previously read:

Primary Contact:

Alternate Contact:

Has been changed to read:

Primary Contact:

Alternate Contact:

Section 8.1.2.1 Primary Efficacy Endpoints

First paragraph, last sentence previously read:

The number and percentage of subjects achieving SVR_{12} will be summarized along with a two-sided 95% confidence interval using the normal approximation to the binomial distribution, unless the rate for SVR_{12} is 100%, where the Wilson's score method will be used for the confidence interval instead.

Has been changed to read:

The number and percentage of subjects achieving SVR₁₂ will be summarized along with a two-sided 95% confidence interval using the normal approximation to the binomial distribution, unless the number of SVR₁₂ non-responders is less than 5, where the Wilson's score method will be used for the confidence interval instead.

Section 15.0 Reference List
Reference 10 previously read:

AbbVie. ABT-493/ABT-530 Fixed-Dose Combination Investigator's Brochure Edition 1. 23 September 2015.

Has been changed to read:

AbbVie. Glecaprevir/Pibrentasvir Fixed-Dose Combination Investigator's Brochure Edition 2. 06 September 2016; including Addendum 1 Edition 2. November 2016.

Appendix C. Study Activities – Treatment Period

Header row previously read:

Activity	Screening	Day 1 ^a	Wk 1	Wk 2	Wk 4	Wk 8*	Wk 8 EOT or Wk 12 EOT* or Premature D/C from Treatment ^b
----------	-----------	--------------------	------	------	------	-------	---

Has been changed to read:

Activity	Screening	Day 1 ^a	Wk 1	Wk 2	Wk 4	Wk 8	Wk 8 EOT or Wk 12 EOT* or Premature D/C from Treatment ^b
----------	-----------	--------------------	------	------	------	------	---

Appendix C. Study Activities – Treatment Period

Activity "Vital Signs, Weight, Waist Circumference, Height^e" and "HCC Screening Liver ultrasound and Alpha Fetoprotein^m" previously read:

Activity	Screening	Day 1 ^a	Wk 1	Wk 2	Wk 4	Wk 8*	Wk 8 EOT or Wk 12 EOT* or Premature D/C from Treatment ^b
Vital Signs, Weight, Waist Circumference, Height ^e	X	X	X	X	X	X	X
HCC Screening Liver ultrasound and Alpha Fetoprotein ^m	X						

Has been changed to read:

Activity	Screening	Day 1 ^a	Wk 1	Wk 2	Wk 4	Wk 8	Wk 8 EOT or Wk 12 EOT* or Premature D/C from Treatment ^b
Vital Signs, Weight, Waist Circumference, ^e Height ^e	X	X	X	X	X	X	X
HCC Screening Liver ultrasound ^m	X						

Appendix C. Study Activities – Treatment Period

Table note "m." previously read:

Child-Pugh Score, Clinical Assessment of Hepatic Decompensation, Liver Ultrasound, and Alpha Fetoprotein are only performed for subjects in Arm B (compensated cirrhotic) as described in Section 5.3.1.1.

Has been changed to read:

Child-Pugh Score, Clinical Assessment of Hepatic Decompensation, and Liver Ultrasound are only performed for subjects in Arm B (compensated cirrhotic) as described in Section 5.3.1.1.

Appendix D. Study Activities – Post-Treatment (PT) Period
Delete: Activity "Alpha Fetoprotein^e"

Activity	PT Wk 4	PT Wk 12	PT Wk 24 or PT D/C ^a
Alpha Fetoprotein ^e		X	

Appendix D. Study Activities – Post-Treatment (PT) Period
Add: Activity "HCC Screening Liver Ultrasound"

Activity	PT Wk 4	PT Wk 12	PT Wk 24 or PT D/C ^a
HCC Screening Liver Ultrasound			X ⁱ

3.0 Introduction

This statistical analysis plan (SAP) describes the statistical analyses to be completed by the AbbVie Statistics and Statistical Programming Departments for glecaprevir (GLE)/pibrentasvir (PIB) study Protocol M16-126. Study M16-126 evaluates the efficacy and safety of GLE/PIB in HCV treatment-naïve or treatment-experienced (i.e., has failed prior interferon [IFN] or pegylated-IFN [pegIFN] with or without ribavirin [RBV], or sofosbuvir [SOF] plus RBV with or without pegIFN therapy), chronic hepatitis C virus (HCV) genotype (GT) 5 or 6-infected subjects, without cirrhosis for an 8-week treatment duration or with compensated cirrhosis for a 12-week treatment duration.

This SAP (Version 1.0) provides details to further elaborate the statistical methods outlined in Clinical Study Protocol M16-126 incorporating Amendment 1 dated 28 July 2017, and describes analysis conventions to guide the statistical programming. Unless noted otherwise, all analyses will be performed using SAS[®] Version 9.4 (SAS Institute Inc., Carry, NC 27513) or later under the Unix operating system.

The SAP will not be updated in the case of future administrative or minor amendments to the protocol unless the changes have any impact on the analysis of study data.

4.0 Study Objectives, Design and Procedures

4.1 Objectives

The primary objectives of this study are to assess the efficacy (by evaluating the percentage of subjects achieving a 12-week sustained virologic response, SVR₁₂) and safety of GLE/PIB in adults with chronic HCV GT5 or 6 infection with or without compensated cirrhosis.

The secondary objectives are to assess the efficacy of GLE/PIB in adults with HCV GT 5 or 6 infection with or without compensated cirrhosis by evaluating the percentages of subjects with on-treatment virologic failure and post-treatment relapse.

[figure not shown]
4.2 Design Diagram

Study M16-126 is a Phase 3b, open-label, nonrandomized, multicenter study to evaluate the efficacy and safety of GLE/PIB in adults with chronic HCV GT5 or 6 infection, without cirrhosis or with compensated cirrhosis, who are either treatment-naïve or treatment-experienced with IFN or pegIFN with or without RBV or treatment-experienced with SOF plus RBV with or without pegIFN.

The study will enroll approximately 80 eligible subjects. A minimum of 15 GT5 and 30 GT6 subjects and up to approximately 16 subjects with compensated cirrhosis (regardless of GT) will be enrolled. Each subject will be assigned to one of two treatment arms based on their cirrhosis status. Non-cirrhotic subjects (Arm A) will be treated with GLE/PIB 300 mg/120 mg once daily for 8 weeks, while subjects with compensated cirrhosis (Arm B) will be treated with GLE/PIB 300 mg/120 mg once daily for 12 weeks.

Scheduled visits for subjects in the Treatment Period consist of Day 1 and Weeks 1, 2, 4, and 8 for all subjects and an additional Week 12 visit for subjects in Arm B. Subjects who complete or prematurely discontinue study drug will be followed for 24 weeks. During the Post-Treatment Period, all subjects will have visits at Post-Treatment Weeks 4, 12, and 24.

Figure 1. Study Schematic

4.3 Sample Size

In Phase 2 and 3 studies, Study M14-868 and Study M14-172, GT 5 and 6 subjects were enrolled to demonstrate the pangenotypic efficacy of GLE/PIB across GT1-6 for the label

approved treatment duration. The current study, Study M16-126, serves to generate additional efficacy and safety data from GT 5 and 6 subjects in a wider geographic region. Therefore, no formal hypothesis will be tested in this study. The sample size of this study is determined based on operational considerations of enrolling subjects with less common HCV genotypes.

If the observed SVR₁₂ rate in this study is 97% among the expected 30 GT5 and 50 GT6 subjects, then the expected 95% confidence intervals (CIs) for the SVR₁₂ rate using the Wilson's score method¹ are (84.2%, 99.3%) and (88.2%, 99.1%), respectively, based on the Wilson's score CIs calculated for 1000 simulated samples of 30 GT5 and 50 GT6 subjects with an SVR₁₂ rate of 97% using SAS[®]. The Wilson's score method is expected to be used instead of the normal approximation method because the number of SVR₁₂ non-responders is expected to be less than 5 (see Section 10.3).

4.4 Planned Analyses

All analyses will be conducted by statisticians and programmers at AbbVie or designees according to the methodologies specified in this SAP.

The primary analysis will occur after all subjects have completed the Post-Treatment Week 12 Visit or prematurely discontinued from the study. For the primary analysis, data will be locked after performing appropriate data cleaning. Results from the primary analysis (e.g., SVR₁₂ data) will be described in the primary clinical study report (CSR).

The end-of-study analysis will be conducted when all subjects enrolled in the study have completed the Post-Treatment Week 24 Visit or prematurely discontinued from the study. Data collected after the primary analysis will be added to a new version of the database which will be cleaned and locked at the end of the study and included in the final CSR (results related to SVR₁₂ will not be updated).

There is no intention of stopping the study early based on efficacy findings from the primary analysis. The intention is to follow all subjects who receive study drug for 24 weeks following treatment.

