8.0 Statistical Methods and Determination of Sample Size

8.1 Statistical and Analytical Plans

The primary analysis will occur after all subjects have completed the PT Week 12 Visit or prematurely discontinued treatment. The data for the primary analysis will be locked after data cleaning. Data after PT Week 12 will be added to a new version of the database which will be cleaned and locked at the end of the study.

SAS[®] (SAS Institute, Inc., Cary, NC) for the UNIX operating system will be used for all analyses. All confidence intervals will be two-sided with an alpha level of 0.05.

Descriptive statistics will be provided, such as the number of observations (N), mean, and standard deviation (SD) for continuous variables and counts and percentages for discrete variables.

Safety, and demographic analyses will be performed on all subjects who receive at least one dose of study drug.

Efficacy analyses will be performed on the intention-to-treat (ITT) population defined as all enrolled subjects who receive at least one dose of study drug, unless otherwise specified.

Sensitivity analyses of the primary efficacy endpoint, when applicable, will be performed on the intention-to-treat population modified to exclude subjects not of GT5, 6 according to phylogenetic analyses (mITT-GT), and on the mITT-GT population further modified to exclude subjects who did not achieve SVR₁₂ for reasons other than virologic failure (mITT-GT-VF).

No data will be imputed for any efficacy or safety analysis except for analyses of SVR endpoints (HCV RNA data). HCV RNA values will be selected for the analyses of all SVR endpoints (e.g., SVR₄, SVR₁₂, and SVR₂₄) based on defined visit windows. A backward imputation method will be used to impute missing responses for SVR analyses.

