6.3 Missing Data Imputation

Missing Data Imputation for SVR

HCV RNA values will be selected for analysis based on the analysis windows defined in Section 6.2.

For analyses of SVR, subjects' missing visit values will have backward imputation applied, if possible. For backward imputation, if the nearest HCV RNA value after the SVR window is unquantifiable or undetectable, then it will be used to impute the HCV RNA value in the SVR window. If a subject is missing an HCV RNA value within the appropriate SVR window after performing backward imputation, then this value will be imputed with an HCV RNA value from a local laboratory if present; otherwise, the HCV RNA value will be missing. Subjects with missing HCV RNA data in the analysis window, after imputations, will be imputed as a failure.

Regardless of the imputation method described above, if a subject starts another treatment for HCV, then all HCV RNA values for this subject measured on or after the start date of the new HCV treatment will be excluded from analyses. The subject will be considered a failure for summaries of viral response at all time points after the start of the new HCV treatment.

Missing Data Imputation for Virologic Failure

If HCV RNA values from the central laboratory are missing but a local laboratory value is present in the appropriate time period, then the local laboratory value will be used to assess post-treatment relapse and on-treatment virologic failure.

Missing Data Imputation for PRO Questionnaires

The handling of missing data for PROs will be as follows. If a respondent answers at least 50% of the items in a multi-item scale of the Short Form 36 Version 2 (SF-36v2) Health Status Survey, the missing items will be imputed with the average score of the answered items in the same scale. In cases where the respondent did not answer at least

50% of the items, the score for that domain will be considered missing. The Mental and Physical Component Summary measures will not be computed if any domain is missing. Missing data handling conventions for scores related to the Work Productivity and Activity Impairment Questionnaire (WPAI) – Hepatitis C are specified in Section 10.9.

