8.1 Disposition of Safety Population

The number of subjects in each of the following categories will be summarized by investigator for each treatment arm and overall.

- Subjects enrolled in this study;
- Subjects who took at least one dose of study drug;
- Subjects who completed study drug;
- Subjects who prematurely discontinued study drug;
- Subjects who completed the study;

- Subjects who prematurely discontinued from the study;
- Subjects ongoing in the Post-Treatment Period (if applicable at the time of analysis).

The number and percentage of subjects who discontinued study drug will be summarized by reason (all reasons) and by primary reason (per eCRF) for each treatment arm and overall. Similar summaries will be provided for discontinuations from the study.

The number and percentage of subjects with reported study drug interruptions will be summarized by treatment arm and overall. Reasons for study drug interruptions will be presented in the CSR listings.

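### SVR12 is frozen at the Week 12 lock although its imputation rule can need a later sample, so an occasional subject's result depends on last-dose date relative to the lock (minor)

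*SAP*

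**What the plan says.** **Imputation.** For a subject with no HCV RNA value in the SVR12 window, SAP 6.3 looks forward: "if the nearest HCV RNA value after the SVR window is unquantifiable or undetectable, then it will be used to impute" the missing one. If that yields nothing, "then this value will be imputed with an HCV RNA value from a local laboratory if present". Failing that, "Subjects with missing HCV RNA data in the analysis window, after imputations, will be imputed as a failure".

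**Windows and visits.** SAP 6.2, Table 2 sets the SVR12 window at Study Drug End Days 57 to 126 (nominal Day 84) and the SVR24 window at Days 127 to 210 (nominal Day 168). Under SAP 4.2, "all subjects will have visits at Post-Treatment Weeks 4, 12, and 24". No sample is scheduled between Weeks 12 and 24.

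**Lock.** SAP 4.4: "The primary analysis will occur after all subjects have completed the Post-Treatment Week 12 Visit or prematurely discontinued from the study". Data collected afterwards go into a new database version and are "included in the final CSR (results related to SVR₁₂ will not be updated". Protocol 8.1 words the trigger differently: "The primary analysis will occur after all subjects have completed the PT Week 12 Visit or prematurely discontinued treatment".

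**What the SAP foresees.** The disposition table in SAP 8.1 has a row for "Subjects ongoing in the Post-Treatment Period (if applicable at the time of analysis". The non-response categories in SAP 10.1 include treatment completers who still have no SVR12-window value after imputation.

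**The concern.** The imputation rule can require a sample taken after Day 126, while the lock is tied to a visit at nominal Day 84 and closes SVR12 for good. Neither document restricts the rule to data that every subject could have by the lock, and neither reopens SVR12 when the later data arrive.

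Two subjects with the same record (nothing usable in Days 57 to 126, then a Week 24 result below LLOQ) can therefore be classified differently. The one whose Week 24 sample is already in the database is a success. The one still in follow-up is a permanent failure. The difference comes from calendar time and has nothing to do with the drug.

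At stake are the primary ITT proportion in each genotype and the end-of-study concordance of SVR12 with SVR24 (SAP 10.7). In the concordance table the frozen failure would sit beside an SVR24 success.

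**Working it through.** **1. Check of the method on the plan's own figures.** SAP 4.3 gives expected 95% Wilson intervals at a 97% rate of (84.2%, 99.3%) for n = 30 and (88.2%, 99.1%) for n = 50, from 1000 simulated samples. Averaging the Wilson limits exactly over Binomial(n, 0.97) gives (84.1%, 99.2%) and (88.2%, 99.1%), which agree to within 0.1 point. The documents give no figure for the timing question itself.

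**2. Who has a usable later sample at the lock.** Suppose data are cut when the last subject is at Study Drug End Day C. A subject whose last dose was s days earlier then has C + s days of follow-up. A sample just outside the window needs C + s ≥ 127; the nominal Week 24 visit needs C + s ≥ 168.

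| Cut C | s needed for Day 127 | s needed for Day 168 |
|---|---|---|
| 84 | 43 | 84 |
| 126 | 1 | 42 |
| 168 | 0 | 0 |

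The lock date is not stated. The asymmetry at nominal Week 24 disappears only if the cut is at Day 168 or later.

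**3. How many subjects.** Let m be the share with no usable value in Days 57 to 126 and f the share with no Week 24 sample at the cut. Neither is in the documents; I assume m = 1% to 5% and f = 10% to 50%, independent of each other. The expected number exposed is 80 × m × f:

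- low: 80 × 0.01 × 0.10 = 0.08; chance of at least one = 1 − (1 − 0.001)^80 = 8%
- high: 80 × 0.05 × 0.50 = 2.0; chance of at least one = 1 − (1 − 0.025)^80 = 87%

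These are upper figures for actual misclassification, because the later sample must also be below LLOQ.

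**4. Effect of one subject.** The shift in the proportion is 1/n: 1/30 = 3.3 points in GT5 and 1/50 = 2.0 points in GT6. The Wilson limits are [p + z²/2n ± z√(p(1−p)/n + z²/4n²)] / (1 + z²/n), with z = 1.96. For 29/30 the centre is (0.9667 + 0.0640)/1.1280 = 0.914 and the half-width is 0.080, giving 83.3% to 99.4%.

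| Group | Without the artefact | With one artefact |
|---|---|---|
| GT5, no other failure | 30/30 = 100% (88.6–100) | 29/30 = 96.7% (83.3–99.4) |
| GT5, one other failure | 29/30 = 96.7% (83.3–99.4) | 28/30 = 93.3% (78.7–98.2) |
| GT6, no other failure | 50/50 = 100% (92.9–100) | 49/50 = 98.0% (89.5–99.6) |
| GT6, one other failure | 49/50 = 98.0% (89.5–99.6) | 48/50 = 96.0% (86.5–98.9) |
| GT5 at its minimum of 15 | 15/15 = 100% (79.6–100) | 14/15 = 93.3% (70.2–98.8) |

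Backward imputation applies only when the later value is unquantifiable or undetectable, so it only ever creates successes. Withholding it can only lower SVR12.

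**5. Concordance.** At 97% about 80 × 0.03 = 2.4 failures are expected overall. Suppose two subjects truly fail at both time points and all others are concordant. The negative predictive value is then 2/2 = 100%; one frozen failure with SVR24 success makes it 2/3 = 67%. If the artefact is the only SVR12 failure, it is 0/1 = 0%.

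**The case against.** **The trigger, read literally, protects the late subject.** Someone who misses Week 12 but stays in the study has neither completed that visit nor left, so the SAP lock would wait; if the subject leaves before Day 127, no later value will exist anyway. This narrows the point but does not remove it. A subject who skips Week 12 and finishes at Week 24 would never satisfy the literal trigger, so in practice it must count a visit that has been passed. A subject who attends Week 12 but whose sample is lost or unusable satisfies it on any reading.

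**Missing the visit is not enough.** This stands. A reader might infer that every late enrollee who misses Week 12 becomes a failure. The documents do not support that. The window is 70 days wide, a local laboratory value is accepted, and the lock must also precede a later sample that proves to be below LLOQ.

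**Such a subject would be visible.** SAP 10.1 has a category for missing window data, SAP 10.3 lists non-responders by reason, and SAP 10.7 reports SVR24 by genotype. That is true and limits the harm. But mITT-GT-VF only drops the subject, and the alternative interval in SAP 10.5 uses the same count. Neither restores the primary ITT result.

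**Freezing a primary result at its lock is legitimate, and later re-derivation can only turn failures into successes.** Both statements are correct. They are the reason to leave the primary result alone and to pre-specify the re-derivation as supplementary, with both results shown.

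**Conclusion.** SAP 4.4 and 6.3 do not fit together for a subject still in follow-up at the lock with no usable value in Days 57 to 126, and a rule is needed. The point is minor. It probably concerns 0 to 2 of 80 subjects, at 3.3 points each in GT5 or 2.0 in GT6 if the planned numbers are reached. That count rests on assumed rates of missing values and an assumed lock date, and its range includes no effect at all.

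Two stronger readings should be resisted. A reader might infer a material bias in the primary result. The direction is conservative, no hypothesis is tested (SAP 4.3), and the number exposed is small. A reader might also infer from Protocol 8.1 that the lock can precede Week 12 for subjects who stop treatment early and remain in follow-up. That wording would permit it, but the SAP, which elaborates the protocol's methods, uses the stricter condition of leaving the study. The difference is not listed in SAP 12.1 and is a matter of alignment.

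**What to change.** Keep the SVR12 result from the primary lock as the primary result. In SAP 4.4, replace the parenthesis with text along these lines:

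> The SVR12 result from the primary lock remains the primary result. As a supplementary analysis at end of study, SVR12 will be re-derived for subjects who had no SVR12-window HCV RNA value at the primary lock, applying Section 6.3 unchanged. Both results will be shown in the final CSR, and the re-derived result will be used for the concordance of SVR12 with SVR24. A missed visit or an unusable sample at Post-Treatment Week 12 is handled in this way.

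Also align the trigger in Protocol 8.1 with the SAP, so that it refers to discontinuation from the study.

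The cost is a few sentences and one table re-run. The downside is a possible footnoted difference between the primary and final CSRs.
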